### **CONFIDENTIAL**

This document is confidential and the property of individual. No part of it may be transmitted, reproduced, published, or used by other persons without prior written authorization from the author.

any SAEs are detected, observed by or reported to the investigator at any time outside of a regularly scheduled visit, they have to be reported by the investigator according to Section 6.4.

**Table 5-1 Recommended Data Collection Schedule**

	Baseline	Observation period	End of study
Timing of data collection	Day 0	At least one visit. Recommended at Every Visit.	12 months± 7 days
Informed Consent	X		
Eligibility	X	X	
Demographics	X		
Non-ocular and ocular medical history/comorbidities	X		
Tobacco use history	X		
Prior and concomitant Systemic medications	X	X	X
Prior ocular treatments / Therapies	X	X	X
Visits performed between this and last documented visit that was not reported as part of the study		X	X
Ocular examination (e.g. Slit lamp examination, IOP)*	X	X	X
Visual acuity in ETDRS or Snellen (preferably BCVA)	X	X	X
Central retinal thickness	X	X	X
Ranibizumab treatment Given #	X	X	
Use of antimicrobials*	X	X	
SAEs § /AEs	X	X	X

\* optional, according to the investigator's routine clinical practice

# treatment patterns according to each investigator's routine clinical practice

§ whenever any SAEs are detected, observed by or reported to the investigator at any time outside of a regularly scheduled visit, have to be reported by the investigator according to Section 6.4.

## **5.1 Baseline Visit**

### **5.1.1 Informed consent procedures**

Eligible patients may only be included in the study after providing a written informed consent or, if incapable of doing so, after such consent has been provided by a legally acceptable representative of the patient. In cases where the patient's representative gives consent, the patient should be informed about the study to the extent possible given his/her understanding. If the patient is capable of doing so, he/she should indicate assent by personally signing and dating the written informed consent document or a separate assent form. Informed consent must be obtained before conducting any data collection (i.e. all of the procedures described in the protocol). The process of obtaining informed consent should be documented in the patient source documents.

#### **5.1.1.1 Patient numbering**

Each patient is identified by a unique patient identification code, which is only used for study purposes. This code is a number that results from the combination of his or her center number and patient number. Each study center will be identified with a two digit center number. The center number is assigned by the Contract Research Organization (CRO) to the study site.

Upon signing the informed consent form, the patient is assigned a patient number by the investigator. At each study site, the first patient is assigned patient number 1 and subsequent patients are assigned consecutive numbers (e.g., the second patient is assigned patient number 2, the third patient is assigned patient number 3 etc). Once assigned to a patient, a patient number will not be re-used.

For the duration of the study and afterwards, only the patient's investigator is able to identify the patient based on the patient identification code.

### **5.1.2 Verification of patient's eligibility**

Determine patient's eligibility based on inclusion/exclusion criteria. See sections 4.1 and 4.2

#### **5.1.2.1 Information to be collected on screening failures**

Not applicable.

### 5.1.3 Patient demographics and other baseline characteristics

At baseline, patients' demographic variables and information about their medical and ocular history, comorbidities and concomitant medication will be collected from the treating physician. The investigator collects data regarding patient's medical and ocular history from medical records if available, or else by interviewing the patient. More precisely, the following data elements will be collected at baseline:

- Date of visit (DD/MM/YYYY)
- Demographic data (e.g., date of birth, gender, race/ethnicity)
- Non-ocular medical history/comorbidities (based on historical data, current treatment, or clinical judgment), including
  - Cardiovascular/Cerebrovascular events, including
    - Myocardial infarction
    - Stroke
    - Thromboembolic event
  - Obesity
  - Family history of coronary artery disease
  - Hypercholesterolemia/hyperlipidemia
  - Hypertension
  - Diabetes
- Ocular Medical History
  - Date of diagnosis of neovascular AMD leading to inclusion in the study
  - Eye diagnosed with neovascular AMD
  - Type of CNV
  - Study eye selection in case of bilateral neovascular AMD
  - Any ocular surgeries and date of surgery
  - Any other eye diseases and conditions
- Smoking history

#### CONFIDENTIAL

This document is confidential and the property of individual. No part of it may be transmitted, reproduced, published, or used by other persons without prior written authorization from the author.

- Prior and concomitant systemic medications (all medications started prior to commencement of ranibizumab and in addition to ranibizumab respectively). Information on concomitant medication to be collected includes:
  - Name of drastic substance
  - Indication
  - Start date
  - Stop date or “continued”
  - Dosage
- Any prior or concomitant ocular treatments including
  - Indication
  - Eye(s) treated
  - Name of drastic substance
  - Start date
  - Stop date or “continued”
  - Dosage

All the relevant information has to be entered in the Demographics and Medical History/Comorbidities pages of the electronic CRFs. Drugs administered prior start of the study and other drugs continuing or started during the study period will be entered on the Prior and concomitant medications electronic CRF page.

#### **5.1.4 Ocular examination**

Ocular examination of the study eye including slit-lamp examination, fundoscopy and IOP measurement are considered optional and may according to the investigator's routine clinical practice. If available, the collected data will be entered in the Ocular Examination page of the electronic CRF.

#### **5.1.5 Visual acuity**

Effectiveness of ranibizumab treatment will be described by change in VA of the study eye from baseline. Effectiveness cannot be described if VA at baseline is missing. Therefore it is recommended to document VA in the Visual Acuity page of the electronic CRF at the Baseline visit.

#### **CONFIDENTIAL**

This document is confidential and the property of individual. No part of it may be transmitted, reproduced, published, or used by other persons without prior written authorization from the author.

Visual acuity (preferably BCVA) of the study eye will be measured according to the method used by the treating physician in the course of local routine care. Visual acuity will be captured in the electronic CRF, allowing use of ETDRS-like or Snellen charts. If a Snellen fraction or decimal score is entered, it will be converted into an approximate ETDRS equivalent letter score for the purpose of statistical analysis. Therefore, it is recommended that ETDRS-like sight charts are used if available.

For consistency and analyses, it is recommended that the same method of VA assessment be used throughout the study wherever possible. Progression or no progression of the disease activity will be evaluated at each visit from study entry.

### **5.1.6 Central retinal thickness as evaluated with OCT**

In addition to VA, effectiveness of ranibizumab treatment will also be measured anatomically by change in CRT in the study eye as this is evaluated with OCT.

Effectiveness regarding this anatomical parameter cannot be evaluated if CRT value at baseline is missing. Therefore it is recommended to document it in the OCT page of the electronic CRF at the Baseline visit. Whenever CRT is measured with the OCT it is recommended to enter the data in the relevant page of each visit in the electronic CRF.

For consistency and analyses' purposes, it is recommended that the same method of assessment and the same type of OCT machine be used throughout the study wherever possible.

### **5.1.7 Treatment**

This is an open-label, observational study to assess effectiveness of ranibizumab treatment of neovascular AMD in routine clinical practice. There is no therapy being prescribed or dispensed as part of this study. This observational study does not direct therapy nor recommends any treatment for neovascular AMD. All the patients enrolled will receive ranibizumab as treatment for neovascular AMD. The only study's recommendation for dose, frequency, or duration of treatment is that patients should be treated with ranibizumab according to the approved local ranibizumab SPC. The decision on the duration and frequency of treatment is solely at the discretion of the attending investigator.

In Greece Lucentis® is available as 10 mg/ml ranibizumab solution for injection in a single-use vial or as a 10 mg/ml solution for injection in a pre-filled syringe for single use. It is at the discretion of the investigator to chose or not the pre-filled syringe.

#### **CONFIDENTIAL**

This document is confidential and the property of individual. No part of it may be transmitted, reproduced, published, or used by other persons without prior written authorization from the author.

Information regarding ranibizumab administration during the study will be collected on the Drug Administration page of the electronic CRF. The volume injected and type of the drug formulation administered will also be recorded. Any topical administration of antimicrobial agents pre- or post-injection is optional, depending on the investigator's preference and will be reported.

### **5.1.8 Adverse events and serious adverse events**

Safety evaluations will comprise of the monitoring and assessment of all systemic and ocular AE occurring during the study. Any relationship of an AE with the study drug will be assessed and indicated by the investigator.

These relevant data will be collected according to the schedule detailed in Table 5-1 and are required to be entered in the Adverse Event page of the electronic CRF. See section 6.

## **5.2 Observational period**

There is no preset visit schedule during the observational period. The visit frequency should be dictated by the local standard of care as this is determined by each investigator individually at each site. At least one visit between Baseline and EOS visit is required to be performed and reported in order to maintain a patient's participation in the study. However, it is recommended to report the data from every visit that will take place during the observational period.

Typical information to be collected during a visit during observational period includes:

- Date of follow-up visit (DD/MM/YYYY)
- Confirmation of patient's eligibility based on inclusion/exclusion criteria.
- Concomitant medications (systemic and ocular)
- Any visits performed between this and last documented visit that was not reported as part of the study
  - Number of visits
  - Date of visit (precise or approximate)
  - Administration of treatment or not
- Ophthalmic examination
- Visual acuity

#### **CONFIDENTIAL**

This document is confidential and the property of individual. No part of it may be transmitted, reproduced, published, or used by other persons without prior written authorization from the author.

- Central retinal thickness as evaluated with OCT
- Administration of ranibizumab or not. The reason for administration or not of ranibizumab (i.e., VA, OCT findings, or a combination of the above) must be described on the electronic CRF. See section 5.1.7.
- Adverse events and serious adverse events. See section 6.

### **5.3 End of study visit**

The EOS visit has to be performed at 12 months  $\pm$  7 days from baseline visit. Typical information to be collected at EOS visit includes:

- Date of follow-up visit (DD/MM/YYYY)
- Concomitant medications (systemic and ocular)
- Any visits performed between this and last documented visit that was not reported as part of the study
  - Number of visits
  - Date of visit (precise or approximate)
  - Administration of treatment or not
- Ophthalmic examination
- Visual acuity
- Central retinal thickness as evaluated with OCT
- Adverse events and serious adverse events. See section 6.

### **5.4 Withdrawal Visit**

Not applicable.

### **5.5 Unscheduled Visit**

Not applicable.

### **5.6 Other study procedures/evaluations**

#### **5.6.1 Laboratory Procedures/Evaluations**

Not applicable.

## 5.6.2 Questionnaire Administration

Not applicable.

# 6 Safety monitoring and assessment

The safety recording period starts after providing informed consent from the patient.

## 6.1 Adverse event

An AE is the appearance of any sign(s), symptom(s), or medical condition(s) or the worsening of any pre-existing undesirable sign(s), symptom(s), or medical condition(s) occurring after signing the informed consent during the safety recording period even if the event is not considered to be related to ranibizumab.

The occurrence of AEs should be sought by non directive questioning of the patient at each visit during the study. Adverse events also may be detected when they are volunteered by the patient during or between visits or through physical examination, laboratory test, or other assessments provided by the patient. Clinically significant abnormal laboratory values or test results should be identified through a review of values outside of normal ranges or clinically notable ranges, significant changes from Baseline or the previous visit, or values which are considered to be non-typical in patient with underlying disease. Investigators have the responsibility for managing the safety of an individual patient and identifying clinically significant AEs.

Once an AE is detected, it should be followed until its resolution or until it is judged to be permanent, and assessment should be made at each routine visit (or more frequently, if necessary) of any changes in severity, the suspected relationship to ranibizumab, the interventions required to treat it, and the outcome.

Physicians will be encouraged to follow-up with patients who have not been seen in the clinic for at least 3 months since the last visit to capture any AEs that may have occurred since the previous visit, and again 3 months later if no subsequent visit occurs within the following 3 months.

### CONFIDENTIAL

This document is confidential and the property of individual. No part of it may be transmitted, reproduced, published, or used by other persons without prior written authorization from the author.

Information about common side effects and adverse reactions observed with ranibizumab can be found in the approved ranibizumab SPC. This information will be also included in the patient informed consent and should be discussed with the patient during the study as needed.

## **6.2 Reporting an adverse event**

All AEs occurring during the safety recording period will be collected and -irrespective of any suspected causal association to ranibizumab administration- be recorded in the Adverse Event Report Form which is appended to the electronic CRF within 7 calendar days of awareness. Report of an AE should be accompanied by the following information:

- severity grade (mild, moderate, severe)
- location (non-ocular, left eye, right eye, both eyes)
- relationship to ranibizumab or to the procedure of the ocular injection (suspected or not suspected). Possibly related means that there is a reasonable possibility that the incident, experience, or outcome of the AE may have been caused by the ocular injection or ranibizumab.
- duration (start and end dates or if continuing at final examination)
- whether it constitutes an SAE
- action taken
  - no action taken (i.e., further observation only)
  - study drug dosage adjusted or temporarily interrupted
  - study drug permanently discontinued due to this AE
  - concomitant medication given
  - non-drug therapy given
  - patient hospitalized or patient's hospitalization prolonged.

## **6.3 Serious adverse event**

As SAE defined an AE which:

- results in death
- is life-threatening (places the subject at immediate risk of death from the event as it occurred)

### **CONFIDENTIAL**

This document is confidential and the property of individual. No part of it may be transmitted, reproduced, published, or used by other persons without prior written authorization from the author.

- results in persistent or significant disability or incapacity
- constitutes a congenital anomaly or birth defect
- requires inpatient hospitalization or prolongation of existing hospitalization

**Unlike routine safety assessments, SAEs are monitored continuously and have special reporting requirements; see Section 6.4.**

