**CONFIDENTIAL**

This document is confidential and the property of individual. No part of it may be transmitted, reproduced, published, or used by other persons without prior written authorization from the author.

trial EXCITE (22) demonstrated that participants who after three monthly, loading doses received quarterly injections of ranibizumab showed improvement of vision but not to the level achieved by the monthly regimen. The above trial found that intravitreal injections of ranibizumab given quarterly were clearly superior to treatment with sham (MARINA) or verteporfin photodynamic therapy (ANCHOR) in patients with CNV secondary to AMD but that treatment scheme was unable to deliver the same improvement in vision as the monthly treatment. Additionally, patients treated with ranibizumab reported large improvement in near vision, distance vision and vision-specific dependency as indicated by the NEI-VFQ-25 (23).

The topical route of administration of ranibizumab through intravitreal injection is considered to minimize potential systemic effects of anti-VEGF agents such as ranibizumab that are used to treat neovascular AMD. However, intraocular administered drugs could enter the systemic circulation, despite the presence of the blood-retinal barrier, which shields the retina from circulating blood. Several prospective, randomized clinical trials have demonstrated that intravitreal therapy with ranibizumab is generally well tolerated. However, within these trials, there is some circumstantial evidence that links systemic VEGF inhibition to systemic adverse events, particularly systemic thromboembolic events.

For instance, in the phase 3 ANCHOR and MARINA trials, intravitreal ranibizumab injections were associated with a low rate of ocular AEs, including endophthalmitis, uveitis, and transient increases in intraocular pressure (IOP). In these trials, a slightly increased but still low rate of systemic AEs, like Antiplatelet Trialists' Collaboration arterial thromboembolic events (APTC ATEs) (i.e. nonfatal myocardial infarction, stroke, and vascular death) and nonocular hemorrhages, were reported (14, 15).

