## 4 Population: study enrollment and withdrawal

The study population will consist of patients diagnosed with neovascular AMD at one eye and who have not received any prior treatment for the particular condition. The decision of the investigator to treat neovascular AMD with intravitreal injections of ranibizumab has to be taken before the evaluation of the patient's eligibility for inclusion in the study.

During the study period it is planned to collect valid documentations on treatment of neovascular AMD from a representative sample of approximately 251 patients who meet the specific for study eligibility criteria and are treated at outpatient level in 10 Ophthalmology Departments of public hospitals or private eye centers of Greece.

Eligible patients must fulfill **all** the inclusion criteria and **none** of the exclusion criteria.

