## **6.4 Serious adverse event reporting**

To ensure patient safety, **every SAE**, regardless of suspected causality, occurring after the patient has provided informed consent and until 30 days after the patient has stopped study participation (defined as time of last dose of ranibizumab taken during the study or last visit whichever is later) **must be reported to the Sponsor within 24 hours of learning of its occurrence**. Any SAEs experienced after this 30 day period should only be reported to the Sponsor if the investigator suspects a causal relationship to ranibizumab. Information about all SAEs is collected and recorded on the Serious Adverse Event Report Form. The investigator must assess the relationship of any SAE to ranibizumab, complete the SAE Report Form in English and send by fax or e-mail the completed, signed form within 24 hours of learning of its occurrence to Sponsor. The original copy of the SAE Report Form and the fax confirmation sheet or email receipt confirmation must be kept with the case report form documentation at the study site. A SAE that is considered completely unrelated to a previously reported one should be reported separately as a new event.

The outcome of all reported SAEs (resolution, death etc.) will be followed up and documented. Recurrent episodes, complications or progression of the initial SAE must be reported as follow-up to the original episode, regardless of when the event occurs. Follow-up information is sent within 24 hours of the investigator receiving the follow-up information using a new SAE Report Form stating that this is a follow-up to the previously reported SAE and giving the date of the original report. The follow-up information should describe whether the event has resolved or continues, if and how it was treated, and whether the patient continued or withdrew from study participation.

If the SAE is unexpected, i.e. not previously documented in the local product SPC and is thought to be related to ranibizumab, the Sponsor may urgently require further information from the investigator for Health Authority reporting.

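### The SAE definition in Section 6.3 has no medically-important-event criterion, so a sight-threatening ocular event managed without admission and without persistent or significant disability is classed as non-serious

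*Protocol*

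**What the plan says.** Section 6.3 of the protocol lists what makes an adverse event (AE) serious. There are five criteria:

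1. it "results in death";
2. it "is life-threatening (places the subject at immediate risk of death from the event as it occurred");
3. it "results in persistent or significant disability or incapacity";
4. it is a congenital anomaly or birth defect;
5. it "requires inpatient hospitalization or prolongation of existing hospitalization".

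The list then closes and the text turns to reporting.

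Two clocks depend on this classification. Under Section 6.4 an SAE "must be reported to the Sponsor within 24 hours of learning of its occurrence". Under Section 6.2 any AE, whatever its suspected cause, is recorded on the AE form "within 7 calendar days of awareness".

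Section 8.4.1 counts patients with any serious AE and patients with any non-serious AE separately, and tabulates AEs by seriousness among other headings.

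On the expected events, Section 1.1 says that the pivotal trials showed a "low rate of ocular AEs, including endophthalmitis, uveitis, and transient increases in intraocular pressure (IOP"). On the setting, Section 4 says that patients "are treated at outpatient level in 10 Ophthalmology Departments of public hospitals or private eye centers of Greece".

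**The concern.** The treatment is an injection into the eye, so the complications of most interest are ocular. The seriousness criteria are general ones. The life-threatening criterion is restricted to immediate risk of death, so a threat to sight cannot enter there. Apart from resulting disability, the only criterion that an ocular complication could readily meet is hospitalisation, and that depends on whether the patient is admitted.

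Two things are at stake. The first is speed: an event that threatens sight but does not meet Section 6.3 does not reach the sponsor by the 24-hour route. Nor does it fall under the Section 6.4 provision for urgent further information on unexpected, related events, which is written for SAEs. The second is classification: the serious and non-serious columns of the safety tables would separate clinically similar ocular events according to admission, or to how an investigator reads the word significant for vision.

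**Working it through.** No formula is involved. The check applies the definition to one case and follows the result into reporting and analysis.

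**Step 1. Apply Section 6.3.** The case is an ocular event such as endophthalmitis or uveitis that threatens sight, is managed without admission, and is treated with vision kept or recovered before any persistent or significant disability results.

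| Criterion in Section 6.3 | Met? |
|---|---|
| Death | No |
| Immediate risk of death | No; sight is at risk, not life |
| Persistent or significant disability | No, by the terms of the case |
| Congenital anomaly or birth defect | No |
| Inpatient hospitalisation or its prolongation | No; not admitted |

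The result is zero of five, so the event is not an SAE.

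**Step 2. Look for a sixth criterion elsewhere.** Section 6.1 makes investigators responsible for identifying clinically significant AEs but does not tie this to seriousness. Section 6.2 asks whether the event is an SAE but adds no definition. Section 6.4 uses the term as defined in 6.3. The synopsis adds nothing. No section has a criterion for medical importance, threat to sight, or intervention needed to prevent one of the listed outcomes.

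**Step 3. Follow the label into reporting.**

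| | Classed as SAE | Not classed as SAE |
|---|---|---|
| Route | SAE form to the sponsor (6.4) | AE form in the electronic CRF (6.2) |
| Time from awareness | 24 hours | up to 7 calendar days |

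The difference is up to 7 − 1 = 6 days.

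**Step 4. Follow the label into analysis.** Under Section 8.4.1 the patient is counted among those with a non-serious AE and, absent any other SAE, is left out of the serious count. The event still appears among the ocular AEs of the study eye. Its severity, location, relationship to the drug or to the injection procedure, and action taken are all recorded under Section 6.2.

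**Step 5. Size.** The protocol gives no incidence for endophthalmitis or uveitis beyond calling the rate low, no share of such events managed without admission, and no expected SAE rate. The number of patients affected therefore cannot be derived. What can be said is the effect per patient: with all 251 planned patients in the denominator, one reclassified patient with no other SAE changes the proportion with any serious AE by 1/251 = 0.004, or 0.4 percentage points.

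**The case against.** The strongest case against the point has five parts.

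- **Loss of sight need not be permanent to qualify.** A reader might infer that an outpatient ocular event becomes serious only once permanent loss is shown. The text does not say so. The disability criterion is met by persistent or by significant disability, so significant visual loss can qualify when it occurs, even if it later recovers. This stands, and it narrows the gap to events that have caused neither. What remains is that significant is not defined for vision, so borderline cases rest on each investigator.
- **The safety objective is not undercounted.** A reader might infer that the secondary safety result misses injection-related events. Sections 2.2 and 2.3.2.1 define that objective by the type, frequency, severity and relationship of AEs, not by SAE incidence. The events stay in those data. This stands; the fault is in the label and the timing.
- **The outpatient setting does not show how complications are managed.** Section 4 describes where patients receive treatment for macular degeneration. Sites include public hospitals, and the AE form has an action category for hospitalisation. This stands. The point therefore applies to events managed without admission, however many those are.
- **The effect on the SAE count may be small.** The count planned in Section 8.4.1 is of patients with any serious AE, without separating ocular from non-ocular. Section 1.1 cites two-year arterial thromboembolic event rates of 4.4% to 5.0% in the ranibizumab arms, so non-ocular events may make up much of that figure. This stands, and a claim that the SAE proportion would change severalfold has no support in the document.
- **The protocol does not contradict itself.** It applies one definition throughout. This also stands. The case for change is that the definition fits poorly with the route of administration and the risks that the protocol itself names.

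One further reply, that the matter can wait for the statistical analysis plan, does not hold. The investigator assigns seriousness when the event is reported, and a 24-hour report that was never sent cannot be recovered at analysis.

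**Conclusion.** The point holds in a limited form. Section 6.3 leaves out any medically-important-event criterion. A sight-threatening ocular event managed without admission, and without persistent or significant disability, is therefore non-serious: it has up to 7 calendar days instead of 24 hours, and it sits in the non-serious column of the Section 8.4.1 tables.

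This conclusion rests only on the protocol's own list, its two reporting clocks and the ocular risks that it names. It assumes that at least some such events are managed without admission, which the protocol neither states nor excludes. Its frequency is unknown. The primary analysis and the overall ocular AE results are unaffected. The defect is one of delayed notification and inconsistent seriousness classification, and it is worth correcting because the correction is short and has to be in place before events are reported.

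**What to change.** Add a sixth criterion to Section 6.3 and to the SAE form: an event that the investigator judges medically important, including a sight-threatening ocular event or one that needs intervention to prevent an outcome already listed. Section 6.4 and the seriousness tables in Section 8.4.1 refer to SAEs as defined, so they take up the change without further text.

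The cost is one line in the protocol and one on the form, a few more expedited reports, and some added investigator judgement. The hospitalisation criterion stays, so some dependence on site admission practice remains. Naming sight-threatening ocular events means that admission would no longer decide the classification of those events. The change concerns reporting only and alters no treatment or visit.
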